The follow-up period will last 5 years, and during that time we will observe how many cases of IMD occur in each cohort to stablish the effectiveness of Bexsero vaccination.

Concurrently, we will collect information about adverse reactions due to vaccination registered in each cohort, in order to compare it.

STUDY POPULATION

The target population of the study are children (boys and girls) aged among 3 months to 5 years old, who are attending to Public Health System and whose data about visits and vaccinations are registered into the SIDIAP.

Inclusion criteria

- Children aged among 3 months and 5 years old.
- Health Centres that participate in the study register patient's information into SIDIAP database.

Exclusion criteria

- Children that are not receiving regularly vaccines.
- Previous antecedent of meningococcal meningitis or sepsis.
- Children with one of the following pathologies: *

Persistent complement deficiencies.

Primary or secondary immunodeficiencies.

Anatomical or functional asplenia.

*The reason why it is necessary to exclude those children is because they have different vaccination regimens from those of the general population.

SAMPLE PROTCOL

Sample selection

The sample will be selected, taking into account the mentioned inclusion and exclusion criteria, from registers contained into SIDIAP database. A non-probabilistic consecutive sampling method is employed in this study.

All children that accomplish previously mentioned criteria will be included.

The enrolment period starts on June 2017 and finishes on June 2018, lasting 1 year.

The desired follow- up for each participant should be 5 years, because this is the period where higher incidence rates occur among paediatric population.

Sample size

The application "GRANMO" has been used to calculate the sample size required. The ARCSINUS approximation has been used.

Accepting an alpha risk of 0.05 and a beta risk of 0.10 in a bilateral contrast, we need 14.108 vaccinated children (cohort 1) and 70.540 unvaccinated children (cohort 2) to detect statistically significant differences, considering an efficacy of Bexsero greater than or equal to 70%.

The incidence of IMD in unvaccinated children has been obtained from official data published by "Red Nacional de Vigilancia epidemiológica (RENAVE)" and is 16 cases /100.000 hab per year.

Dropout rate is estimated as 5%.

STUDY VARIABLES

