- Adverse reactions registered: it is a dichotomous qualitative variable. It is registered as presence of adverse reaction associated with vaccination (Yes or No). It will be described by percentages.

Covariables:

- Sex: it is a dichotomous qualitative variable, described by percentages.
- Age: it is a discrete quantitative variable, defined by mean and standard deviation if it is normally distributed or by median and quartiles in case of non-normal distribution. It will be expressed a confidence interval of 95%.
- Ethnicity: it is a categorical qualitative variable, described by percentages.
- Socioeconomical status: it is a discrete quantitative variable and it will be described by mean and standard deviation if it is normally distributed or by median and quartiles in case of non-normal distribution. It will be expressed a confidence interval of 95%.

BIVARIANT ANALYSIS

To compare the independent variable, which is categorical qualitative, with the main dependent variable, which is discrete quantitative, we will use the Mann-Withney test.

To compare the independent variable with the secondary dependent variable, which are both categorical qualitative we will use the Chi ² test.

To compare qualitative variables between them we will use Chi² test, and to compare quantitative variables between them the Pearson rank or Spearman rank, depending if they are normally distributed or not.

MULTIVARIANT ANALYSIS

It will be used a Cox model adjusted for Propensity Score punctuation, for confounding variables.

ETHICAL AND LEGAL CONSIDERATIONS

The present protocol will be presented for its approval to the Comité d'Ètica i Investigació Clínica (CEIC) de l'Institut d'Investigació i Recerca en Atenció Primària Jordi Gol.

Moreover, we will present that protocol to the Agencia Española del Medicamento y Producto Sanitario (AEMPS) since this is a post-authorisation observational study and it has to be classified.

Once we have obtained the Ethics Commitee's approval and the AEMPS's classification, we present the protocol to the Departament de Salut de Catalunya- Subdirecció General de Recerca i Innovació en Salut, since we are using a vaccine which is a drug.

Finally, in a voluntary way, we will register that protocol to the European Network of Centres for Pharmacoepidemiology and Pharmacovigilance (ENCePP) in order to avoid a possible publication bias.

The project will guarantee that the following considerations and legislations are respected:

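### The stated 90% power comes from an arcsine formula that no planned analysis uses; at the stated cohort sizes Mann-Whitney has about 71% power and a Cox likelihood-ratio test about 78%

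*Protocol*

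**What the plan says.** The Sample size section of the protocol reads: "Accepting an alpha risk of 0.05 and a beta risk of 0.10 in a bilateral contrast, we need 14.108 vaccinated children (cohort 1) and 70.540"; the last figure is the size of the comparison cohort. It assumes an efficacy of at least 70%, an incidence in unvaccinated children of 16 cases per 100,000 per year, and 5% dropout. It does not say whether the stated numbers already allow for dropout. The software was GRANMO, and "The ARCSINUS approximation has been used". Follow-up is 5 years.

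The analysis section uses other methods. Under Bivariant analysis the exposure is compared with the number of IMD cases, "which is discrete quantitative, we will use the Mann-Withney test". Under Multivariant analysis: "It will be used a Cox model adjusted for Propensity Score punctuation, for confounding variables". The protocol does not say which of the two tests the primary hypothesis, and nothing links the arcsine calculation to either.

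**The concern.** Sizing a study with a simple two-proportion formula and analysing it with something else is usually harmless, because the common tests agree closely when both groups have enough events. Here allocation is 1:5, the assumed effect is strong, and only three or four cases are expected in the vaccinated cohort. In that region the arcsine, score, likelihood-ratio and Wald tests separate, and a power figure for one cannot be carried over to another.

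At stake is how a null result would be read. The section on impact to the National Health System says that if the vaccine proves not useful this should be known, so that healthy children are not given it. A reader who believes the 90% would expect a truly 70%-effective vaccine to be missed 1 time in 10. On the protocol's inputs the miss rate is roughly 2 to 3 in 10, depending on the analysis.

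**Working it through.** **Inputs (Sample size section).** Two-sided alpha 0.05; power 0.90; n1 = 14,108; n0 = 70,540 (ratio 5); efficacy 0.70; 16 per 100,000 per year; 5 years. Assuming a constant rate, p0 = 5 × 0.00016 = 0.0008 and p1 = 0.30 × 0.0008 = 0.00024. Expected cases are 14,108 × 0.00024 = 3.39 and 70,540 × 0.0008 = 56.43.

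**Step 1: the plan's own figure.** The arcsine difference is d = 2·asin(√0.0008) − 2·asin(√0.00024) = 0.05658 − 0.03099 = 0.02559.

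- Required size: n1 = (1 + 1/5) × ((1.960 + 1.2816)/0.02559)² ≈ 19,254, with 5 × 19,254 = 96,270 unvaccinated. The stated 14,108 is not reproduced; the formula needs 36% more.
- Power at the stated size: d/√(1/14,108 + 1/70,540) = 2.775, and Φ(2.775 − 1.960) = 0.792. After 5% loss it is 0.772.
- The nearest simple arcsine match is 80% power without dropout (14,382), which contradicts the stated beta of 0.10.

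**Step 2: the planned tests at the stated size.** I enumerated the two binomial case counts exactly and counted rejections in the protective direction at |z| ≥ 1.96. With x1 and x0 cases:

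- Mann-Whitney: IMD is in effect 0/1 per child, so the tie-corrected test is the score (Pearson) test, z = (x1/n1 − x0/n0)/√(p̄(1−p̄)(1/n1 + 1/n0)).
- Cox, likelihood-ratio: approximated by 2[x1·ln(x1/e1) + x0·ln(x0/e0)], where e1 and e0 are the cases expected under no effect.
- Cox, Wald: approximated by ln(rate ratio)/√(1/x1 + 1/x0), with zero vaccinated cases counted as no rejection.

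| Test | 14,108 + 70,540 | after 5% loss | 19,254 + 96,270 |
|---|---|---|---|
| Arcsine formula | 79.2% | 77.2% | 90.0% |
| Mann-Whitney/score | 70.7% | 67.8% | 86.3% |
| Cox, likelihood-ratio | 78.4% | 76.0% | 90.3% |
| Cox, Wald | 62.2% | 57.8% | 83.5% |

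**Step 3: splitting the shortfall.** From the stated 90% to the arcsine 79.2% is about 11 points, and this comes from the stated size. From 79.2% to 70.7% is about 8 points, which is the mismatch for Mann-Whitney. At the size the arcsine formula really needs, that mismatch is about 4 points (90.0 − 86.3). For a Cox likelihood-ratio test it is under 1 point at either size.

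**Step 4: type I error at the stated size, protective tail (nominal 2.5%).** Likelihood-ratio 2.9%, score 1.8%, Wald 1.4%. The likelihood-ratio test's other tail is 2.3%, so its two-sided total is about 5.2%.

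**Step 5: zero vaccinated cases.** exp(−3.39) = 0.034.

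**The case against.** Most of the gap has another cause, and this stands. A reader might infer that the choice of test alone takes power from 90% to 62–71%. The documents do not support that: 11 of those 19 to 28 points come from a sample size that its own formula does not reproduce.

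A reader might also take 62% as the power of the planned Cox analysis. The protocol names no Wald test. That figure rests on a common software default, and the choice between Wald and likelihood-ratio can reasonably be left to an analysis plan. With a likelihood-ratio test, equally compatible with the text, the mismatch for the Cox model all but disappears. Only the Mann-Whitney figure follows directly from the protocol's words.

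Nor is the 16-point difference between likelihood-ratio and Wald a pure gain. The tests differ in protective-tail error (2.9% against 1.4%), so part of it reflects how conservative the Wald test is here.

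Someone could apply the Schoenfeld formula to the 59.8 expected events: √(59.8 × 1/6 × 5/6) × |ln 0.30| − 1.96 = 1.51, or 93% power. It is unreliable here because it splits the events as if there were no effect (about 10 vaccinated cases), whereas about 3.4 are expected under the stated efficacy.

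Finally, the inputs matter more than the test. The protocol enrols all eligible children and hopes for more than the required number, so realised power could be higher. Its Epidemiology section, however, gives 8 per 100,000 under 1 year and 2.18 under 5 years. At 8 per 100,000 throughout, Mann-Whitney power at the stated size would be about 31%. This limits the precision of the figures above but does not rescue the stated beta of 0.10.

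**Conclusion.** The point holds in a limited form. None of the analyses considered delivers 90% power at 14,108 + 70,540 on the protocol's inputs. Mann-Whitney has about 71% (68% after 5% loss). The Cox model has about 78% (76%) with a likelihood-ratio test, and about 62% (58%) only if a Wald test is used. The mismatch between sizing method and test accounts for about 8 points for Mann-Whitney at the stated size, about 4 at the corrected size, and almost nothing for a Cox likelihood-ratio test. The remaining 11 points or so belong to the unreproduced sample size.

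Correcting the arcsine calculation alone would therefore still overstate the power of Mann-Whitney, at 86% rather than 90%. The figures assume a constant rate over 5 years, at most one case per child, and a rate-ratio approximation to the Cox model. Propensity adjustment is not modelled, because the protocol gives nothing to model it with.

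**What to change.** In the Sample size section, name the analysis that tests the primary hypothesis and replace the 90% with that analysis's power at 14,108 + 70,540: about 71% for Mann-Whitney/score, or about 78% for Cox with a likelihood-ratio test. Both are before loss, so state the 5%-loss figures (68% and 76%) beside them.

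If the Cox model is primary, specify the likelihood-ratio test for the Bexsero term and a profile-likelihood 95% confidence interval for the hazard ratio. These remain usable with no vaccinated case (probability about 3.4%), where a Wald analysis gives no finite estimate. State that the protective-tail type I error is about 2.9%, against 1.8% for score and 1.4% for Wald, so part of the power gain reflects the conservatism of the other tests.

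The cost is a few sentences, a standard software option and a less favourable stated power; no children or data are added. If the sponsor prefers to keep beta at 0.10, the size must be recomputed for the named analysis. Before loss and at 1:5, that is about 19,254 vaccinated for the likelihood-ratio test, and between 21,000 (89.5%) and 22,000 (91.1%) for Mann-Whitney.

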Hence, given the lack of information about Bexsero the Spanish Vaccinology Association and the Health Ministry (14) as well as work groups for Bexsero's use in special situations (28) have elaborated several documents and recommendations about the use of the vaccine. Together, those entities do not recommend a systematic use of Bexsero.

On the contrary, pediatricians and the Vaccine Advisory Committee of the Spanish Pediatrics Association ⁽¹⁵⁾ advise a routinary use of Bexsero and encourage parents to vaccinate children. In fact, they are asking for introduce Bexsero into the routine vaccination schedule.

Furthermore, other European countries such as Italy (11), France (32) have found different results when they asses the effects of Bexsero in its population.

Recently, United Kingdom has introduced Bexsero as a routine vaccine and, since 2015, they are collecting data about its effectiveness in their population.

In conclusion, given the existing controversies about Bexsero use and the lack of strong evidences about its real efficacy in IMD prevention; further studies are required to really know the effects of that vaccine.

For that reason, the aim of this protocole is designing a study that assesses, mainly, the effectiveness of Bexsero for prevent IMD in children aged among 3 moths and 5 years old, since those are the most affected for this disease and, in addition, there are no studies performed in that age group. Moreover, it will also provide information about its adverse reaction profile.

HYPOTHESIS

PRIMARY

Children under 5 years old who have been vaccinated with Bexsero have lower incidence of invasive meningococcal disease in comparison with unvaccinated children.

SECONDARY

Children under 5 years old vaccinated with Bexsero as well as routinary vaccines show a higher proportion of adverse reactions than those who just receive routinary vaccinations.

OBJECTIVES

MAIN OBJECTIVE

❖ To asses the effectiveness of Bexsero in prevention of invasive meningococcal disease in children aged among 3 months and 5 years old.

SECONDARY OBJECTIVES

❖ To compare the occurrence of adverse reactions among children vaccinated with routinary vaccines and Bexsero versus children vaccinated with routinary vaccines.

METHODOLOGY

STUDY DESIGN

This is an observational prospective cohort study. It will have two groups:

- ❖ Cohort 1: it will include children vaccinated with Bexsero.
- ❖ Cohort 2: it will include children non vaccinated with Bexsero.

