Finally, the outcome variable for the secondary objective are adverse reactions due to vaccination.

^{*} Criteria must be present.

Adverse reaction: it is defined as a harmful and undesirable reaction which is produced with normal doses used in humans for prevent, diagnose or treat a disease.

We consider adverse reactions all reactions, local or systemic, caused by vaccinations:

Local adverse reaction: local pain, cutaneous erythema, swelling.

Systemic adverse reaction: Fever >38°C, irritability, bad general condition.

Information about adverse reactions is codified as **T66**.

Covariables: it is important to control several factors that may interfere with the possibility of a child receives or not the vaccine.

Those variables will be:

Sex: Male or Female.

Age: measured in months and years.

Ethnicity: Caucasian, Asian, Afro-American and others.

Socioeconomical status: according with MEDEA index included into SIDIAP and expressed in percentiles.

DATA COLLECTION

Data will be obtained from SIDIAP (Sistema d'Informació pel Desenvolupament de la Investigació en l'Atenció Primària). That database integrates information from several sources, but mainly from e-CAP, which collects information belonging to Primary Attention, and CMBD (Conjunt Mínim Bàsic de Dades), which contains information from Hospital registers like admission diagnosis, patient's evolution, complications, reasons of discharge, etc. However, there are other information sources into SIDIAP database.

Those data represent nearly an 80% of population in Catalunya.

Through SIDIAP we can access to demographical information such as sex, age, race, socioeconomical status, etc; as well as information about health problems, results of complementary tests and therapeutically procedures or vaccinations received by the patient.

VARIABLE DESCRIPTION AND STATISTICAL ANALYSIS

UNIVARIANT ANALYSIS

❖ Independent variable: it is a dichotomous qualitative variable. It is registered as: Vaccinated or Unvaccinated and described with percentages.

❖ Dependent variables:

- Number of cases of invasive meningococcal disease: it is a discrete quantitative variable. It is defined by mean and standard deviation if it is normally distributed or by median and quartiles in case of non-normal distribution. It will be expressed a confidence interval of 95%.

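### The single Yes/No safety outcome answers the secondary hypothesis but cannot tell serious from mild reactions, so it cannot supply the adverse reaction profile the protocol promises

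*Protocol*

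**What the plan says.** All references are to the protocol.

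- **Study variables, outcome for the secondary objective.** The definition is inclusive: "We consider adverse reactions all reactions, local or systemic, caused by vaccinations". The local signs are "local pain, cutaneous erythema, swelling" and the systemic signs are "Fever >38°C, irritability, bad general condition". No grade, seriousness criterion or admission criterion is given. One code is named: "Information about adverse reactions is codified as" T66.
- **Univariant analysis.** The local and systemic groups become one variable: "It is registered as presence of adverse reaction associated with vaccination (Yes or No"), described by percentages.
- **Bivariant analysis.** For the vaccination variable and the safety variable, "which are both categorical qualitative we will use the Chi ² test".
- **Hypothesis and Objectives.** The secondary hypothesis is a higher proportion with adverse reactions in the Bexsero cohort. The secondary objective is to compare their occurrence.
- **Justification.** The stated aim goes further: "Moreover, it will also provide information about its adverse reaction profile". Safety is listed among the unknowns that motivate the study.
- **Data collection.** The source database includes the CMBD, "which contains information from Hospital registers like admission diagnosis". Study variables already uses hospital codes 036.0, 036.2 and 036.3 for the primary outcome.
- **Impact to the National Health System.** An association between Bexsero and more adverse reactions is expected to alter existing advice on the vaccine and to prompt further research.

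**The concern.** A profile describes which reactions occur and how serious they are. A single ungraded Yes/No holds neither piece of information. The protocol separates local from systemic reactions in its definition and then drops the separation in the analysis. It never separates serious reactions at all.

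Two consequences follow. First, if the chi-square test shows an excess, the protocol expects recommendations to change, yet the variable could not say whether the excess was redness at the injection site or hospital admission. Second, a child already recorded as Yes for a mild reaction contributes nothing more if a serious one follows. If recorded mild reactions greatly outnumber serious ones, a real change in serious reactions is diluted.

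The protocol itself fixes the variable, the code and the test, so this is not a detail left to a later analysis plan.

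**Working it through.** **No figure to reproduce.** The protocol's only sample size calculation is for invasive meningococcal disease. It gives no rate, effect size or power for adverse reactions. The check takes the stated cohort sizes as given and assumes reaction rates over a range.

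**Inputs from the protocol (Sample size):** n1 = 14,108 vaccinated, n2 = 70,540 unvaccinated, two-sided α = 0.05.

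**Assumptions:** recorded mild risk m, equal in both cohorts; serious risk s in cohort 2 and 2s in cohort 1; mild and serious reactions independent; every serious reaction recorded under T66; no continuity correction; no dropout.

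**Formulas.** Merged Yes/No: p1 = 1 − (1 − m)(1 − 2s) and p2 = 1 − (1 − m)(1 − s). Separate serious outcome: p1 = 2s and p2 = s. With d = p1 − p2, pooled p = (n1p1 + n2p2)/(n1 + n2), s0 = √[p(1 − p)(1/n1 + 1/n2)] and s1 = √[p1(1 − p1)/n1 + p2(1 − p2)/n2],

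power = Φ[(d − 1.96·s0)/s1] + Φ[(−d − 1.96·s0)/s1].

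**Separate, 0.2% v 0.1%.** Expected children: 14,108 × 0.002 = 28.2 and 70,540 × 0.001 = 70.5. Then s0 = 0.000315, s1 = 0.000395, and (0.001 − 1.96 × 0.000315)/0.000395 ≈ 0.97, so power is 83%.

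**Merged, same doubling, m = 5%.** p1 = 0.05190, p2 = 0.05095, d = 0.00095, s0 = 0.002031, s1 = 0.002043. The first term is Φ(−1.48) = 0.069 and the second 0.008, so power is 8%.

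**Serious 0.1% doubling to 0.2%, across recorded mild rates:**

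| Mild rate, both cohorts | Merged risk ratio | Merged power | Separate power |
|---|---|---|---|
| 0.1% | 1.50 | 63% | 83% |
| 0.5% | 1.17 | 29% | 83% |
| 1% | 1.09 | 18% | 83% |
| 5% | 1.02 | 8% | 83% |
| 10% | 1.01 | 6% | 83% |

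Simulating the two binomial counts gives the same merged values to within about one percentage point, and 84% for the separate outcome.

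**Other serious rates, doubled in cohort 1:**

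- 0.05% to 0.10%: merged 9%, 6% and 5% at mild 1%, 5% and 10%; separate 59%.
- 0.2% to 0.4%: merged 94% at mild 0.1%, 50% at 1%, 10% at 10%; separate 98%.
- 0.5% to 1.0%: merged 98% at mild 1%; separate above 99%.
- 0.01% to 0.02%: separate only about 23%, on roughly 2.8 and 7.1 expected children (22% by simulation).

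**The reverse case.** With mild reactions at 5% v 6% and no serious difference, the merged test is significant with probability 99.7%. With mild at 10% v 11% and serious at 0.1% in cohort 2, power is 94% if serious risk is equal in cohort 1, 92% if halved and 97% if doubled. In that setting the result says almost nothing about serious reactions.

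**The case against.** The strongest reply is that the Yes/No matches the question asked. The hypothesis concerns a proportion with reactions and the objective concerns occurrence; a dichotomous variable with chi-square serves both. The word profile appears once, in the Justification. This stands: the variable is not wrong for the hypothesis, and the test should not be dropped or made merely descriptive.

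The second reply is that the dilution depends on rates nobody has stated. Reactions are those registered in routine records, not solicited by diary, so many sore arms will never be coded and recorded mild rates may be well below 1%. This also stands. At a mild rate of 0.1% the merged test keeps 63% power against 83%. A reader might infer that a doubling of serious reactions must go unseen, or that mild reactions alone must settle the result; the documents support neither as a certainty.

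Third, nothing in the protocol says a null result would be taken as proof of safety, and the Impact section also presents an association as a reason for further research. That is fair, but the same section still ties recommendations to the result.

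Finally, the protocol does not say whether hospitalised reactions receive T66. That limits the power model, but it gives no reassurance: if they do not, the Yes/No misses them altogether.

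What none of this answers is identification. Whatever the rates, an excess on this variable cannot be traced to mild or serious reactions.

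**Conclusion.** The point holds in limited form. The Yes/No answers the secondary hypothesis. It cannot distinguish serious from mild reactions, so it cannot deliver the promised profile, and a change in recommendations would rest on an excess of unknown kind. That part needs no assumption about rates.

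Masking is probable only if recorded mild reactions predominate. For serious reactions going from 0.1% to 0.2%, merged power falls from 63% at a mild rate of 0.1% to 6% at 10%, against 83% when counted separately. These figures rest on assumed rates and on T66 capturing every serious reaction. Separate counting is no cure for very rare events, where the gain is mainly descriptive. A reader might conclude that the safety question cannot be answered in either direction; that goes too far, because the prespecified question about the proportion with any reaction can be answered.

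The point concerns a secondary objective and leaves the primary comparison untouched. It should be corrected before data extraction, since a list of serious diagnoses chosen after seeing the data would carry little weight.

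**What to change.** In Study variables and in the statistical analysis section:

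1. Keep the any-reaction Yes/No and its chi-square test for the secondary hypothesis.
2. Add a prespecified serious-reaction outcome: a CMBD admission with a diagnosis from a code list fixed before extraction, within a fixed window after a vaccine dose. Apply the same list and window to both cohorts; without a window, coincidental admissions over five years would count.
3. Report it by cohort as a risk difference with 95% CI. Allow for the additional dose visits in cohort 1, which otherwise give those children more time inside a window.
4. Report local and systemic reactions separately where the coding allows.
5. State that neither a null any-reaction test nor a wide interval for serious reactions shows absence of a safety difference.

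The cost is protocol wording, one more code list run on a hospital register already read for the primary outcome, and a little more analysis. The drawbacks are a wide interval for a rare outcome and a local/systemic split that depends on coding beyond T66.
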